#### 1. PROTOCOL SYNOPSIS

**Study Title:** A Phase 1/2a Single and Multiple Dose-Escalating Study to Evaluate the Safety, Tolerability, Pharmacokinetics and Pharmacodynamic Effects of ARO-HSD in Normal Healthy Volunteers as well as in Patients with NASH or Suspected NASH

Study Number: AROHSD1001

**Phase:** Phase 1/2a

Number of Sites: One or more sites in Australia, New Zealand, and Asia

#### **Study Treatments:**

There will be two study treatments; one active (Test Formulation) and one placebo (Reference Formulation).

### **Test Formulation:**

The test formulation is active ARO-HSD Injection (also referred to as ARO-HSD). The active pharmaceutical ingredient (API) contained in ARO-HSD is a synthetic, double-stranded, small interfering RNA (siRNA) duplex conjugated to an N-acetyl-galactosamine targeting ligand to facilitate hepatocyte delivery.

#### Reference Formulation:

The reference formulation is placebo (PBO): normal saline (0.9%) administered subcutaneously, volume matched to the corresponding ARO-HSD dose volume.

#### **Study Objective and Endpoints:**

• The objective of the study is to assess the safety and tolerability of ARO-HSD in normal healthy volunteers (NHVs) and patients with NASH or suspected NASH.

#### **Primary Endpoint:**

• The incidence and frequency of adverse events (AEs) possibly or probably related to treatment after single doses in healthy volunteers and after multiple doses in patients with NASH or suspected NASH

## **Secondary Endpoints**

Pharmacokinetics of ARO-HSD

#### **Exploratory Endpoints**

#### (All Cohorts)

 Change in fasting LDL-C, Total Cholesterol, non-HDL-C, HDL-C, VLDL-C, and triglycerides compared to baseline

#### (Patient cohorts 1b, 3band 4b)

- Change in ALT and in AST as a marker of ARO-HSD activity compared to baseline
- Change in cytokeratin-18 compared to baseline
- Change in IL-1 $\beta$ , IL-6, IL-10, INF-gamma, and TNF- $\alpha$  compared to baseline
- Change in retinol and retinol binding protein compared to baseline
- Change in liver fat using MRI-PDFF compared to baseline
- Change in blood exosomal HSD17β13 mRNA levels (if feasible) compared to baseline
- Change in blood exosomal PNPLA3 mRNA levels (if feasible) compared to baseline
- Change in Enhanced Liver Fibrosis (ELF) Score at EOS compared to baseline
- Change in Pro-C3 at EOS compared to baseline
- Liver biopsy derived HSD17β13 mRNA expression compared to baseline
- Liver biopsy derived HSD17β13 protein expression compared to baseline in response to multiple doses of ARO-HSD (if scientifically feasible)
- Liver biopsy derived change in PNPLA3 mRNA expression compared to baseline
- Liver biopsy derived change in PNPLA3 protein expression compared to baseline in response to multiple doses of ARO-HSD (if scientifically feasible)

**Study Population/Patient Number:** This study will be conducted in adult males and females, aged 18 through 65 years (minimum of 19 years of age for NASH or suspected NASH patients) with BMI between 18.0 and 40.0 kg/m^2 enrolled and dosed as follows (see also Cohort Summary below):

NHV Cohorts 1, 2, 3, and 4: Each double-blind cohort will enroll eight (8) subjects (4 active: 4 PBO) with all cohorts planned to receive single escalating doses of ARO-HSD or placebo at dose levels of 25 mg (Cohort 1), 50 mg (Cohort 2),  $\leq$  100 mg (Cohort 3), and  $\leq$  200 mg (Cohort 4). These dose levels represent the highest dose that may be used in the cohort but after Cohort 1, the Data Safety Committee (DSC) may adjust the dose lower if indicated.

• Patient Cohorts 1b, 3band 4b: All patients will have suspected NASH and meet patient entry criteria. Cohorts are open label with up to 6 patients per cohort. All subjects will receive two doses of ARO-HSD at dose levels of 25 mg (Cohort 1b), ≤ 100 mg (Cohort 3b) and ≤ 200 mg (Cohort 4b). These dose levels represent the highest dose that may be used in the cohort but after Cohort 1, the DSC may adjust the dose lower if indicated.

\*Any NASH/Suspected NASH patient already in Screening when a patient cohort has reached capacity (defined as up to six patients who have completed D1 in Cohort 3b and up to six patients who have completed D1 in Cohort 1b), may participate in the study up to an additional two patients per cohort.

#### **Cohort Summary**

Cohort	Population	Blinding	# Subjects	Dosing Schedule
1	NHVs	Double blind	8 (4 active:	25 mg Day 1 only
			4 placebo)	
1b	Patients with suspected NASH	Open Label	up to 6	25 mg Days 1, 29
	(biopsies on screen and day 71)		(all active)	
2	NHVs	Double blind	8 (4 active:	50 mg Day 1 only
			4 placebo)	
3	NHVs	Double blind	8 (4 active:	≤ 100 mg Day 1 only
			4 placebo)	
4	NHVs	Double blind	8 (4 active:	$\leq$ 200 mg Day 1 only
			4 placebo)	
3b	Patients with suspected NASH	Open Label	up to 6	≤100 mg Days 1, 29
	(biopsies on screen and day 71)		(all active)	
4b	Patients with suspected NASH	Open Label	up to 6	≤200 mg Days 1, 29
	(biopsies on screen and day 71)		(all active)	

Approximately 50 subjects may be enrolled in the study (not including replacements or optional expansion cohort).

**Number of Doses per Treatment:** Single dose (Cohorts 1, 2, 3, 4) or two doses (Cohorts 1b, 3b and 4b) dosed 28 days apart

**Study Duration:** For subjects in Cohorts 1 through 4, the duration of the study clinic visits is approximately 158 days from screening to the End-of-Study visit. For subjects in Cohorts 1b, 3b and 4b, the duration of the study clinic visits is approximately up to 173 days from screening to the End-of-Study visit. Additionally, all subjects will have a 90-day post-end of study visit follow-up phone call assessing compliance with contraception.

**Study Confinement:** For all NHV cohorts (1-4), clinical facility confinement will be approximately 3 days for dose administration (Day -1 through 24-hour assessments) with discharge on Day 2. Subjects will return to the clinical facility for outpatient visits per the Schedule of Assessments. Patients in Cohorts 1b, 3b and 4b will be at the facility for approximately 4 hours (2 hours before dosing and 2 hours after dosing) on dosing days.

#### **Study Design/Methods:**

Participants who have signed an EC/IRB-approved informed consent form and have met all the protocol eligibility criteria during screening may be enrolled into the study in a double-blind or open label fashion depending on the cohort. Cohorts 1 through 4 (NHVs) will begin with administration of ARO-HSD or PBO to two sentinel participants (one ARO-HSD, one PBO). Following the Day 3 evaluation in these participants, if there are no significant safety concerns, the remaining participants in the cohort will be treated at the discretion of the Principal Investigator (PI). Dosing of participants will be staggered by at least 30 minutes such that no two participants will be dosed simultaneously. Sentinel dosing is not required in NASH/suspected NASH patient cohorts.

[figure not shown]
Dose levels by cohort are outlined in the Cohort Summary above and Dose Escalation Schedule below. NHV Cohorts 1 through 4 will enroll sequentially with patient cohorts opening for enrollment in a step-wise manner. Screening for all cohorts may begin once Cohort 1 has been opened for enrollment.

Dose escalation will require approval by the DSC based on all cumulative available safety data for prior cohorts, and through at least Day 15 of the current cohort as shown in Figure 1. Based on this cumulative safety data the DSC will vote to approve dose escalation to the next single dose NHV cohort as well as vote to open a NASH/suspected NASH patient cohort at the dose most recently tested in NHVs. Escalation to the next dose level will proceed until the highest planned dose level is completed, or the trial is halted prematurely by the PI, DSC, or Sponsor due to safety or other reasons. Where specified, dose levels represent the highest dose which may be used. The DSC may adjust doses downward if indicated based on review of available safety data and pharmacodynamic data (if available). All subjects who withdraw from the study prior to their End of Study (EOS) visit, for reasons other than an AE, may be replaced.

Cohort 1b (25 mg on Days 1 and 29) will enroll sequentially after Cohorts 3b and 4b are enrolled and will not require DSC approval to initiate enrollment as the dose is lower than the 200 mg top dose used in cohorts 4 and 4b which have already been opened by the DSC.

In double-blind cohorts, treatment un-blinding may occur, at the PI's discretion, only where deemed necessary for treatment of an AE or for a decision to be made regarding trial continuation. After all subjects in double-blinded cohorts have completed their EOS visit (not including the 90-day follow-up call), all blinded cohorts may be unblinded.

Single and multiple doses of ARO-HSD will be evaluated in a sequential manner as shown in the Dose Escalation Schedule.

#### AE monitoring

Safety assessments will include: AEs/SAEs, physical examinations, vital sign measurements (blood pressure, heart rate, temperature, and respiratory rate), ECGs, clinical laboratory tests, concomitant medications/therapy, and reasons for treatment discontinuation. Safety assessments will be performed at specified time points and prior to study completion.

The AE/SAE reporting period for an enrolled participant begins when the participant provides informed consent. Treatment-emergent AEs/SAEs are defined as those following study drug administration or a pre-existing condition exacerbated by study drug. All AEs that occur during the AE reporting period specified in the protocol must be reported to Arrowhead via electronic case report forms within approximately 48 hours. All SAEs that occur during the reporting period, in addition to reporting via electronic case report forms, must also be reported to Arrowhead via the SAE report form within 24 hours of awareness. All AEs/SAEs will be followed until resolution, until the condition stabilizes, until the event is otherwise explained, or until the participant is lost to follow-up. If the PI learns of any SAE, including a death, at any time after a patient has been discharged from the study, and he/she considers the event reasonably related to the investigational product, the PI will promptly notify the Sponsor. Laboratory abnormalities will

be reported as AEs if considered clinically significant by the PI. Laboratory abnormalities not reported as AEs are not to be reported as clinically significant (CS) in the study database.

## Treatment Stopping Rules:

Escalation to the next cohort will proceed according to the study design until the highest planned dose cohort is completed, unless the trial is stopped early by the DSC, PI or Sponsor. A decision to stop the trial early or discontinue drug in an individual subject, group of subjects or to halt enrollment temporarily or permanently may be indicated based on any of the following:

- 1. A serious adverse reaction (i.e., a serious AE [SAE] considered at least possibly related to the IMP administration) in ONE subject; or severe non-serious adverse reactions (i.e. severe non-serious AEs considered as, at least, possibly related to the IMP administration) in TWO subjects in the same cohort, independent of whether or not the events occur within the same system-organ-class.
- 2. One of the following abnormal results at least possibly related to ARO-HSD:
- In NHV cohorts:
  - Treatment emergent AST and/or ALT > 8X ULN which must be confirmed by repeat blood draw within 48 hours of initial results; OR
  - A treatment emergent AST or ALT >3X ULN (must be confirmed on repeat) with a total bilirubin >2X ULN (must be confirmed on repeat); OR
  - o A treatment emergent ALT or AST >3X ULN (must be confirmed on repeat) with symptoms of RUQ pain, fever, rash or eosinophilia; OR
  - A treatment emergent AST or ALT >3X ULN (must be confirmed on repeat) with an INR > 1.5 (must be confirmed on repeat) and which must not be explained by another plausible cause
- See Appendix 16.1 for treatment modification guidelines in subjects/patients (NASH/Suspected NASH patients) with baseline/pre-dose elevated ALT or AST.

If such serious adverse reactions or severe non-serious adverse reactions occur, enrollment and dosing in healthy volunteers will be paused pending a review of safety data and a decision on how to proceed by the DSC.

Sponsor or PI can discontinue any subject at any time with or without DSC consultation. If such events (as described in #1, #2 above) occur and the subject is not discontinued from the study, the reason for not discontinuing the subject will be included in DSC meeting minutes. Including, but not limited to the events listed above, the DSC may pause the study to additional dosing or dose escalation to provide time to evaluate safety data and recommend the action to be taken, which may include, but is not limited to, one of the following:

- Discontinuation of a subject or group of subjects from the study
- The study is stopped immediately with no further dosing
- The study will continue until the current cohort is completed
- The study will continue, but the next dose escalation will be to a level midway between the current level and the next level specified in the Dose Escalation Schedule above
- The study will continue as planned

#### **Study Assessments:**

#### Safety Assessments:

Safety assessments will be performed at specified time points per the Schedule of Assessments and will include the following:

• Vital signs: Resting heart rate, semi-supine systolic/diastolic blood pressure, respiratory rate, oxygen saturation and temperature

- Clinical laboratory measurements (e.g., chemistry including lipase and lipids, hemoglobin A1C, hematology, coagulation, and urinalysis)
- Resting ECG measurements (measured after participant is semi-supine for at least 3 *minutes*)
- At each visit, participants will be asked about concomitant medications/therapy and will be instructed to
  volunteer any information regarding AEs and SAEs that they may have experienced. Any known untoward
  event that occurs beyond the AE reporting period that the PI considers an SAE and possibly related to study
  treatment will be reported to Arrowhead.
- 90-day post-end of study visit pregnancy follow-up phone call assessing compliance with contraception.

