#### Pharmacokinetics & Urine/Plasma Drug Metabolites:

Blood and urine samples will be collected for pharmacokinetic and drug metabolite analysis per the Schedule of Assessments.

Arrowhead Pharmaceuticals, Inc. Protocol No.: AROHSD1001

Table 1 Schedule of Assessments for Cohorts 1-4 Single Dose: NHV

A	Screening						Day 1					24 hr								End of	
Assessment	(Day -45	Pre-	0	15	30		Day 1					post-			Day	Day	Day	Day	Day	Study (or Early Term)	90 days
	Day -1)	dose	min	min		1 hr	2 hr	4 hr	8 hr	12 hr	18 hr		48 hr	Day 8		29			85, 99		after EOS
Visit Window		-2hrs	±2 n	ninutes	s PK c	nly, ±	10 mi	nutes	other j	proced	dures	±1	hr	±2d	±7d						
Informed Consent	X																				
Eligibility Criteria	X																				
Demographics/Medical Hx	X																				
Physical Exam (See Section 10.3.2)	X	X										as needed		as needed	as needed	as needed	as needed	as needed	as needed	X	
BMI	X	X																		X	
Concomitant Meds/Therapies	X	X										X	X	X	X	X	X	X	X	X	
Electrocardiogram (See Section 10.3.3)	X	X				X	X					X	X			X				X	
Urine Pregnancy Test (WOCP) confirmed negative pre-dose	X	X																		X	
FSH (post-menopause)	X																				
Urine Drug Screen	X																				
Vitals (BP, temp, HR, RR, O 2 )	X	X			X	X	X	X	X			X	X	X	X	X	X	X	X	X	
HIV, Hep B, C	X																				
Labs (heme, coag, lipase, chem, lipids)	X	X										X	X	X	X	X	X	X	X	X	
Hemoglobin A1c	X	X																		X	
Blood PK including met ID		X		X	X	X	X	X	X	X	X	X	X	X	X	X					
Urine PK including met ID		spot		Day 1	0-4 h	r, 4-12	hr, 1	2-24 l	r urin	e colle	ections	S	spot	spot	spot	spot					
Urinalysis	X	X										X	X	X	X	X	X	X	X	X	
Administration of ARO-HSD			X																		
Adverse Events Collection	Х –																			X	
Pregnancy phone call																					X

Page 9 of 59

Table 2 Schedule of Assessments for Cohorts 1b, 3b, 4b: Subjects with suspected NASH (biopsies on screen and day 71)

Confidential

Assessment	Screening			Da	y 1		24 hr						End of Study (or	
Assessment	(Day -60	Pre- dose	0 min	30 min	1 hr	2 hr	post- dose	Day 15	Day 29	Day 57	Day 71	Day 85	Early Term) Day 113	90 days after EOS
Visit Window	Day -1)	-2hrs	±2m	nin (PK o	nly), ±10	)min	±1hr	±2d	±2d	±2d	±5d	±2d	±5d	±7d
Informed Consent	X													
Eligibility Criteria	X													
Demographics/Medical Hx	X													
Physical Exam (See Section 10.3.2)	X	X					as needed	as needed	as needed	as needed	as needed	as needed	X	

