#### 10.5 Study Treatment Administration

Appropriately trained employees of the clinical site will administer the study treatment. Each dose will be administered as a single subcutaneous injection. The date, time and location of administration will be recorded in the source notes and witnessed by a second person from the clinical facility. The site of injection will be marked and mapped for later observation. The preferred site of injection is the abdomen. Optional additional sites are the upper arms and thighs.

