# 10.7 Safety Assessments

The safety of ARO-HSD will be evaluated by collection of the following measurements performed at time points as specified in the Schedule of Assessments Tables 1-2):

- Monitoring of AEs/SAEs
- Physical examinations
- Height and weight
- Vital signs including oxygen level
- ECG measurements
- Local Injection Site Reactions
- Clinical laboratory tests (hematology, chemistry, coagulation, urinalysis)
- Concomitant medications/therapy
- Reasons for treatment discontinuation due to toxicity
- Pregnancy test for WOCP

The AE/SAE reporting period for an enrolled participant will begin when the participant provides informed consent. Treatment-Emergent AEs/SAEs will be those defined as following dose administration. All AEs/SAEs that occur during the AE reporting period specified in the protocol must be reported to Arrowhead Pharmaceuticals, Inc., regardless of the relationship of the AE to study treatment. Any known untoward event that occurs beyond the AE reporting period that the PI considers an SAE and possibly related to study treatment will be reported to Arrowhead.

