# 16.2 Local Injection Site Reactions (LISRs)

The following MedDRA Preferred Terms determined by the Sponsor's pharmacovigilance personnel represent the local injection site reaction:

Injection site discomfort	Injection site abscess
Injection site discoloration	Injection site abscess sterile

Injection site erythema	Injection site atrophy
Injection site irritation	Injection site calcification
Injection site inflammation	Injection site cellulitis
Injection site induration	Injection site dermatitis
Injection site pain	Injection site erosion
Injection site oedema	Injection site fibrosis
Injection site pruritus	Injection site indentation
Injection site rash	Injection site necrosis
Injection site urticaria	Injection site nodule
Injection site reaction	Injection site ulcer
Injection site swelling	

LISRs will only include events that start on the day of injection and persist for at least 48 hours post injection (i.e., event onset date on the day of injection and resolution date not on the day of injection or the day after the injection) will be included. Events with onset date on the day of injection and missing resolution date will also be included in the summary.

The following calculation will be utilized to determine the percentage of injections leading to local injection site reactions:

 $(A/B)^*$ , where A = number of injections with a local injection site reactions, and B = total number of injections.

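### Section 10.7 ties injection site reactions to Tables 1-2, but neither table schedules a site check and patients have no planned contact near 48 hours, so LISR ascertainment is loosely defined and unequal between volunteers and patients

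*Protocol*

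**What the plan says.** Protocol Section 10.7 states that safety will be evaluated by "collection of the following measurements performed at time points as specified in the Schedule of Assessments Tables 1-2", and one item on its list is "Local Injection Site Reactions". The synopsis makes the same general promise ("Safety assessments will be performed at specified time points per the Schedule of Assessments and will include the following"), but its own list does not mention the injection site.

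Tables 1 and 2 contain no injection-site row. The row that could capture a reaction is "Adverse Events Collection". Other relevant provisions are:

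- **Risk.** Section 5.7 names injection site reactions as a risk, with grading and photographs as mitigation.
- **Site marking.** Section 10.5: "The site of injection will be marked and mapped for later observation". No time is given for that observation.
- **Elicitation.** In the synopsis, participants are told at each visit to "volunteer any information regarding AEs and SAEs that they may have experienced". Section 11.3 adds that the investigator or a qualified designee evaluates AEs at each visit.
- **Physical examination.** Under Section 10.3.2, examinations after dosing are symptom-directed and as needed until the End of Study (EOS) visit. The abbreviated EOS examination does not list skin.
- **Definition.** Section 11.5.2 requires a duration of at least 48 hours. Appendix 16.2: "LISRs will only include events that start on the day of injection and persist for at least 48 hours post injection". The appendix applies this through recorded onset and resolution dates, and counts day-of-injection events whose resolution date is missing.
- **Analysis.** SAP Section 9.6.1 plans separate tables for injection-site events and for LISRs, including by severity. Appendix 16.2 defines a percentage of injections leading to an LISR.

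**The concern.** Section 10.7 relies on the schedule for the timing of LISR assessment, and the schedule does not supply it. A site that follows Tables 1-2 exactly is never told to look at an injection site about which nobody has complained.

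The LISR definition also depends on when a reaction ended. Volunteers are seen around the deciding time; patients are not. At stake are the LISR tables and the per-injection percentage, for a risk the protocol itself names. Volunteer and patient cohorts share the nominal 25, 100 and 200 mg levels, so readers will naturally set their LISR percentages side by side although the two were ascertained differently. A missed reaction that would have been judged related is also missing from the primary endpoint. Uncertainty about duration alone affects only the LISR classification, because a shorter injection-site event is still tabulated as a treatment-emergent AE.

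**Working it through.** The plan gives no figure to reproduce here. The check compares the visit times in Tables 1-2 with the 48-hour criterion.

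**Visit times.** Hours after dose = 24 × (visit day − dose day), with the tabulated windows.

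| Group and dose | Contact after dosing | Hours after dose (window) |
|---|---|---|
| Volunteers, single dose | 24 hr | 24 (23 to 25) |
| | 48 hr | 48 (47 to 49) |
| | Day 8 ± 2 d | 24 × 7 = 168 (120 to 216) |
| Patients, dose 1 (Day 1) | 24 hr | 24 (23 to 25) |
| | Day 15 ± 2 d | 24 × 14 = 336 (288 to 384) |
| Patients, dose 2 (Day 29) | on site after dosing | about 2 |
| | Day 57 ± 2 d | 24 × 28 = 672 (624 to 720) |

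If dose 2 also moves within its ± 2 day window, the Day 57 visit falls between 24 × (55 − 31) = 576 h and 24 × (59 − 27) = 768 h. After dose 1, patients have no scheduled contact from about 25 h to at least 288 h. After dose 2 they have none from about 2 h to at least 576 h (24 days).

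**What the date rule needs.** Under Appendix 16.2 an event qualifies if it starts on the injection date and does not resolve on that date or the next. The boundary is the midnight that ends the day after injection, which is 48 minus the clock hour of dosing: 40 h after an 08:00 dose, 36 h after a 12:00 dose, 32 h after a 16:00 dose (dosing times assumed). The patients' 24 h visit falls before that boundary. The volunteers' 48 h visit falls after it.

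**Share of injections.** Active injections in volunteers: 4 cohorts × 4 = 16. In patients: 3 cohorts × 6 × 2 = 36. Total: 52.

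- No scheduled contact near 48 h: 36/52 = 69%.
- No 24 h visit either (patient dose 2): 18/52 = 35%.
- If Cohorts 1b and 3b each take the two extra patients that the synopsis allows: (18 + 4) × 2 = 44 patient injections, and 44/(44 + 16) = 73%.

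**Illustration of under-reporting.** P(no LISR seen in a patient cohort) = (1 − rate × reporting)^12.

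| Assumed true rate per injection | 100% reported | 75% reported | 50% reported |
|---|---|---|---|
| 20% | 0.80^12 = 7% | 0.85^12 = 14% | 0.90^12 = 28% |
| 10% | 0.90^12 = 28% | 0.925^12 = 39% | 0.95^12 = 54% |

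The rates and reporting fractions are assumptions. The 12 injections are two each in six patients, so independence is also an assumption. The table shows how sensitive a small cohort is to missed reports; it does not estimate what will happen in this trial.

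**Onset rule.** Appendix 16.2 requires onset on the day of injection. SAP Section 5, read literally, requires onset on the day after the injection. An event with one known onset date cannot satisfy both.

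**The case against.** The strongest reply is that LISRs are a subset of AEs, selected by Preferred Term and dates, so the AE row in both tables is already a scheduled route for collecting them. The Section 10.7 list does not map one-to-one to table rows: reasons for treatment discontinuation have no row either. AEs are evaluated at each visit (11.3), known AEs are followed to resolution (11.6), reported reactions are photographed at reporting and near resolution (11.5.2), and patients stay about 2 h after each dose. A reaction noticed at 2 h, or at 24 h after dose 1, should therefore be followed to a resolution date. The eCRF and manuals, which might prompt a site check, are not available. The SAP also presents volunteers and patients separately and tests no formal hypothesis.

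Much of this stands, and it rules out three stronger readings that a reader might infer:

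- **That the 48-hour criterion can never be observed in patients.** A reaction still present at Day 15 or Day 57 has plainly lasted longer, and the analysis uses recorded dates rather than a 48-hour examination.
- **That LISR data rest only on volunteered reports.** The synopsis sentence is not the whole method, because investigator evaluation, site marking and follow-up are also specified.
- **That mild reactions will be under-counted.** Missing resolution dates count towards LISRs, so the net direction is unknown.

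What the reply does not supply is any instruction to inspect a site with no reported reaction, or any planned contact with patients near 48 h.

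**Conclusion.** The point holds as a gap in data collection that should be closed. Section 10.7 refers to time points that Tables 1-2 do not contain. For a patient reaction that resolves between visits, the date that decides LISR status rests on recall or unscheduled follow-up. With six patients per cohort, this leaves 36 of up to 52 planned active injections (69%) without scheduled contact near 48 h, while every volunteer injection has it.

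The consequence is less reliable LISR data and unequal ascertainment between volunteers and patients. The direction of bias cannot be stated. No planned formal comparison is invalidated, since none exists. The conclusion rests on the visit schedule as printed and on the assumption that no eCRF or manual adds a site check the protocol does not mention.

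**What to change.** 1. Add an injection-site assessment row to the schedule, at visits that already exist. Table 1: 2 h, 24 h, 48 h and Day 8. Table 2: 2 h and 24 h after dose 1, Day 15, and Day 29 before dosing and 2 h after.
2. Add one brief telephone contact two to three days after each patient injection, asking whether any reaction is still present and, if not, when it ended.
3. Record presence or absence, onset date and resolution date on a short form for every injection, so that the per-injection percentage has a complete numerator and denominator.
4. Reconcile the LISR onset rule between Appendix 16.2 and SAP Section 5. Without this, the new data still cannot be classified consistently.

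If patient visits have already taken place, the SAP can still show separately the LISRs that qualify only because the resolution date is missing.

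Cost: one table row, a short form and two calls per patient. The observed rate of mild reactions may rise because they are now looked for.
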